5.3.4 CTCAE grades for laboratory parameters

Table 5-3 CTCAE grades for laboratory parameters (CTCAE Version 5)

Abnormality	Lab parameter	Grade			
		1	2	3	4
Hematology					
Anemia	Hemoglobin (g/L)	<LLN - 100 g/L	<100 - 80 g/L	<80 g/L transfusion indicated	
Platelet count decreased	Platelets (thrombocytes) (10 ⁹ /L)	<LLN-75.0 x 10 ⁹ /L	<75.0 - 50.0 x 10 ⁹ /L	<50.0 - 25.0 x 10 ⁹ /L	<25.0 x 10 ⁹ /L
White blood cell decreased	Leukocytes (WBCs) (10 ⁹ /L)	<LLN - 3.0 x 10 ⁹ /L	<3.0 - 2.0 x10 ⁹ /L	<2.0 - 1.0 x 10 ⁹ /L	<1.0 x 10 ⁹ /L
Neutrophil count decreased	Absolute neutrophil count (10 ⁹ /L)	<LLN - 1.5 x10 ⁹ /L	<1.5 - 1.0 x10 ⁹ /L	<1.0 - 0.5 x10 ⁹ /L	<0.5 x10 ⁹ /L
Lymphocyte count decreased	Absolute lymphocyte count (10 ⁹ /L)	<LLN x 0.8 - 10 ⁹ /L	<0.8 - 0.5 x 10 ⁹ /L	<0.5 - 0.2 x 10 ⁹ /L	<0.2 x 10 ⁹ /L
Lymphocyte count increased	Absolute lymphocyte count (10 ⁹ /L)		>4 - 20 x 10 ⁹ /L	> 20 x 10 ⁹ /L	
Chemistry					

		Grade			
Liver function					
Alanine aminotransferase increased	ALT (SGPT) (U/L)	>ULN - 3.0 x ULN if baseline was normal; >1.5 – 3.0 x baseline if baseline was abnormal	>3.0 - 5.0 x ULN if baseline was normal; >3.0 – 5.0 x baseline if baseline was abnormal	>5.0 - 20.0 x ULN if baseline was normal; >5.0 – 20.0 x baseline if baseline was abnormal	>20.0 x ULN if baseline was normal; >20.0 x baseline if baseline was abnormal
Aspartate aminotransferase increased	AST (SGOT) (U/L)	>ULN - 3.0 x ULN if baseline was normal; 1.5 – 3.0 x baseline if baseline was abnormal	>3.0 - 5.0 x ULN if baseline was normal; >3.0 – 5.0 x baseline if baseline was abnormal	>5.0 - 20.0 x ULN if baseline was normal; >5.0 – 20.0 x baseline if baseline was abnormal	>20.0 x ULN if baseline was normal; >20.0 x baseline if baseline was abnormal
Blood bilirubin increased	Bilirubin (µmol/L)	>ULN - 1.5 x ULN if baseline was normal; >1.0 – 1.5 x baseline if baseline was abnormal	>1.5 - 3.0 x ULN if baseline was normal; >1.5 – 3.0 x baseline if baseline was abnormal	>3.0 - 10.0 x ULN if baseline was normal; >3.0 – 10.0 x baseline if baseline was abnormal	>10.0 x ULN if baseline was normal; >10.0 x baseline if baseline was abnormal
GGT increased	Gamma-glutamyl transferase (GGT) (U/L)	>ULN - 2.5 x ULN if baseline was normal; 2.0 – 2.5 x baseline if baseline was abnormal	>2.5 - 5.0 x ULN if baseline was normal; >2.5 – 5.0 x baseline if baseline was abnormal	>5.0 - 20.0 x ULN if baseline was normal; >5.0 – 20.0 x baseline if baseline was abnormal	>20.0 x ULN if baseline was normal; >20.0 x baseline if baseline was abnormal
Alkaline phosphatase increased	Alkaline Phosphatase (U/L)	>ULN - 2.5 x ULN if baseline was normal; 2.0 – 2.5 x baseline if baseline was abnormal	>2.5 - 5.0 x ULN if baseline was normal; >2.5 – 5.0 x baseline if baseline was abnormal	>5.0 - 20.0 x ULN if baseline was normal; >5.0 – 20.0 x baseline if baseline was abnormal	>20.0 x ULN if baseline was normal; >20.0 x baseline if baseline was abnormal
Renal function Note: A semi-colon (;) indicates 'or' within the description of the grade.					
Creatinine increased*	Creatinine (µmol/L)	>ULN - 1.5 x ULN	>1.5 - 3.0 x baseline; >1.5 - 3.0x ULN	>3.0 baseline; >3.0 - 6.0 x ULN	>6.0 x ULN
Other enzymes					
Serum amylase increased	Amylase (U/L)	>ULN - 1.5 x ULN	>1.5 - 2.0 x ULN; >2.0 - 5.0 x ULN and asymptomatic	>2.0 - 5.0 x ULN with signs or symptoms; >5.0 x ULN and asymptomatic	>5.0 x ULN and with signs or symptoms
Serum amylase** increased	Amylase (U/L)	>ULN - 1.5 x ULN	>1.5 - 2.0 x ULN;	>2.0 - 5.0 x ULN	>5.0 x ULN
Lipids					
Cholesterol high	Cholesterol Total (mmol/L)	>ULN- 7.75 mmol/L	>7.75-10.34 mmol/L	>10.34-12.92 mmol/L	>12.92 mmol/L
Hypertriglyceridemia	Triglycerides (mmol/L)	1.71 - 3.42 mmol/L	>3.42 - 5.7 mmol/L	>5.7 - 11.4 mmol/L	>11.4 mmol/L

Grade

*Highest grade will be assigned if more than one grade criteria are met for an observed value of a patient.

**CTCAE 4.03 definition. For reporting in CSR, the grade definition per CTCAE 4.03 will be used for this parameter only.

5.4 Clinical notable vital signs

Clinically notable vital sign values to be used for this study are listed below.

Vital sign	Notable criteria
Pulse (beats/min, bpm)	>120 bpm Or <50 bpm
Systolic Blood Pressure (mmHg)	>=160 mmHg Or <=90 mmHg
Diastolic Blood Pressure	>=100 mmHg Or <=50 mmHg
Temperature (°C)	>38.3oC (>101 oF)
Body weight (kg)	>=7% from baseline weight

5.5 Statistical models

5.5.1 Primary analysis

The null hypothesis is that there is no difference in the number of Gd-enhanced T1 lesions per scan between ofatumumab and placebo during the core part. The alternative hypothesis is that there is a difference between the 2 treatment groups.

The null hypothesis will be tested using a negative binomial regression model with log-link, each patient's total number of Gd-enhanced lesions during the Core part as the response variable, and natural log of the number of MRI scans as the offset variable to adjust for the different number of MRI scans between patients. The model will include treatment, region (Japan or other countries), and baseline number of Gd-enhanced lesions (0 or ≥ 1) as factors.

The SAS procedure GENMOD will be used to conduct the analysis. In GENMOD, the log of the dispersion parameter will be used (lognb) as an option in model statement. The natural log of number of MRI scans is used as an offset by specifying offset option in the model statement.

5.5.2 Key secondary analysis

For the secondary endpoints Number of new or enlarging T2 lesions on MRI scans and Annualized Relapse Rate (ARR), statistical model is similar with that of the primary endpoints ([Section 5.5.1](#)), in that a negative binominal model is used.

For the secondary endpoint Time to relapse, a Cox proportional hazard model with treatment, region (Japan or other countries), and baseline number of Gd enhancing lesions (0 or ≥ 1) as factors, and number of relapses in previous year and baseline EDSS as covariates will be used to test $H_0: \lambda_o/\lambda_t = 1$ vs. $H_a: \lambda_o/\lambda_t < 1$. Where λ_o and λ_t are hazard of relapse in ofatumumab and placebo groups respectively.

The SAS procedure PHREG will be used to conduct the Cox PH analysis. The SAS procedure LIFETEST will be used to conduct the KM analysis.

5.6 Rule of exclusion criteria of analysis sets

Patient classification in the analysis sets is entirely based on protocol deviation and non-protocol deviation criteria. Details are provided in [Table 5-4](#) and [Table 5-5](#).

Table 5-4 Protocol deviations that cause subjects to be excluded

Deviation ID	Description of Deviation	Exclusion in Analyses
EXCL01	Patients with primary progressive MS or SPMS without disease activity	Excluded from PPS
EXCL02	Patients meeting criteria for neuromyelitis optica	Excluded from PPS
EXCL06	Patients with an active chronic disease (or stable but treated) of the immune system other than MS or with a known immunodeficiency syndrome	Excluded from PPS
EXCL11	Systemic steroid or adrenocorticotrophic hormone treatment within 30 days prior to Screening MRI	Excluded from PPS
EXCL12	Dimethyl fumarate within 1 month prior to randomization	Excluded from PPS
EXCL13	Fingolimod taken within 2 months prior to randomization	Excluded from PPS
EXCL15	Daclizumab within 4 months prior to randomization	Excluded from PPS
EXCL16	Natalizumab treatment within 6 months prior to randomization	Excluded from PPS
EXCL17	Teriflunomide within 3.5 months prior to randomization or 1 month prior to randomization following accelerated elimination procedure and documented teriflunomide plasma level below 0.02 mg/L	Excluded from PPS
EXCL18	Mild to moderately Immunosuppressive / chemotherapeutic medications (e.g. azathioprine, methotrexate) within 6 months prior to randomization	Excluded from PPS
EXCL19	Highly immunosuppressive/chemotherapeutic medications(Mitoxantrone, cyclophosphamide, cladribine)or any B-cell targeted therapy(rituximab, ocrelizumab)or laquinimod within 2 years before randomization	Excluded from PPS
EXCL20	Mitoxantrone with evidence of cardiotoxicity following treatment or a cumulative life-time dose of more than 60 mg/m ² , at any time prior to randomization	Excluded from PPS
EXCL21	Lymphoid irradiation; bone marrow transplantation; other strongly immunosuppressive treatments (with effects potentially lasting over 6 months), at any time prior to randomization	Excluded from PPS
EXCL22	Ofatumumab or alemtuzumab use at any time	Excluded from PPS
EXCL23	Use of other investigational drugs at screening or within the prior 30 days, or five elimination half-lives, or until the expected pharmacodynamics effect has returned to baseline, whichever is longer	Excluded from PPS
EXCL24	History of malignancy of any organ system within the past 5 years, regardless of evidence of local recurrence or metastases.	Excluded from PPS
EXCL46	History of clinically significant CNS disease (e.g. stroke, traumatic brain or spinal injury, history or presence of myelopathy) or neurological disorders which may mimic MS	Excluded from PPS

Deviation ID	Description of Deviation	Exclusion in Analyses
EXCL47	Patients with neurological findings consistent with Progressive Multifocal Leukoencephalopathy (PML) or confirmed PML at Screening	Excluded from PPS
EXCL48	Patients unable or unwilling to undergo MRI scans	Excluded from PPS
EXCL49	History of hypersensitivity to any of the study drugs or to drugs of similar chemical classes	Excluded from PPS
INCL01	Study Informed consent Date = missing	Excluded from All analysis sets
INCL01A	Incorrect ICF procedure	Excluded from All analysis sets
INCL03	No diagnosis of MS as defined by 2010 revised McDonald criteria	Excluded from PPS
INCL05	No appearance of new neurological abnormality or worsening of pre-existing neurological abnormality during the previous 2 years prior to Screening	Excluded from PPS
INCL06	No appearance of MRI activity, namely no appearance of Gd-enhanced T1 lesions or new/enlarging T2 lesions in brain during the previous 1 year prior to randomization	Excluded from PPS
INCL07	Neurologically Unstable (i.e. Clinical relapse) within 1 month prior to randomization	Excluded from PPS
WITH09	Patient withdraws consent but study treatment was not discontinued	Excluded from PPS
WITH11	Patient diagnosed with PML and study treatment was not discontinued	Excluded from PPS
TRT01	Patient received incorrect study drug	Excluded from PPS
TRT02	Patient received damaged or expired study drug	Excluded from PPS
COMD01	Immunosuppressive medicines such as cyclosporine, azathioprine, methotrexate, cyclophosphamide, mitoxantrone or lymphoid irradiation, hematopoietic stem cell transplantation on study treatment	Excluded from PPS
COMD02	Monoclonal antibodies targeting the immune system such as natalizumab, alemtuzumab, daclizumab and B-cell depleting agents such as rituximab, ocrelizumab and obinutuzumab on study treatment	Excluded from PPS
COMD03	Any other immunomodulatory treatment such as fingolimod, interferon beta, glatiramer acetate, dimethyl fumarate, IVIG, plasmapheresis or chronic corticosteroids on study treatment	Excluded from PPS
COMD04	Leflunomide or teriflunomide while taking study treatment	Excluded from PPS
OTH01	EDSS rater acted as a treating physician or treating physician acted as EDSS rater	Excluded from PPS
OTH02	Not following per protocol blinding procedures such that the integrity of the study is compromised	Excluded from PPS

Table 5-5 Patient Classification

Analysis Set	PD ID that cause patients to be excluded	Non-PD criteria that cause patients to be excluded
FAS	INCL01 INCL01A	Not assigned a valid randomization number; Randomization despite screen failure
PPS	As listed in Table 5-4	Not in FAS; Compliance to study drug administration < 80% EDSS baseline value >=7.0
SAF	INCL01, INCL01A	No double-blind study drug taken

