2.2 Analysis sets

Full analysis set (FAS): The FAS comprises all randomized subjects with assigned treatments. Subjects will be analyzed according to the randomized treatment assignment following the intention-to-treat (ITT) principle, even if they actually received no or a different treatment.

The FAS will be used for the summary of demography and baseline characteristics and all efficacy analyses.

Extension FAS (EFAS): The EFAS will include all FAS subjects who received at least one dose of ofatumumab during Extension part. Analyses on EFAS will include *all* available efficacy assessments of the Core and Extension parts.

Per-protocol set (PPS): The PPS is a subset of FAS, consists of all randomized subjects who take at least one dose of study medication and have no major protocol deviations that could confound the interpretation of analyses conducted on the FAS. Major protocol deviations will be determined according to the pre-defined protocol deviation criteria before treatment unblinding (e.g. non-compliance for a large proportion of the time in study). For analyses performed on the PPS, only on-treatment assessments will be used.

The PPS will primarily be used for the supportive analyses of the primary efficacy variable.

Safety set (SAF): The SAF set includes all subjects who received at least one dose of study medication. Subjects will be analyzed according to the actual treatment received. The Safety Set will be used for all safety analyses for Cut-off 1 analysis.

Extension Safety set (ESAF): The ESAF set includes all subjects who received at least one dose of ofatumumab during Extension part. Subjects will be analyzed according to the actual treatment received. The Extension Safety Set will be used for all Cut-off 2 and final safety analyses. Analyses on ESAF will include safety assessments *only under ofatumumab treatment during the Core and Extension parts*.

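### SAP Table 5-5 removes patients randomised despite screen failure from the FAS, which Protocol 9.1 and SAP 2.2 define as everyone randomised

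*SAP*

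**What the plan says.** SAP 2.2 states: "The FAS comprises all randomized subjects with assigned treatments". Protocol 9.1 has the same sentence. Neither sets an eligibility condition. SAP 2.2 adds that subjects are analysed as randomised "even if they actually received no or a different treatment"; the protocol's version of that clause mentions only a different treatment. SAP 2.5.2 runs the primary negative binomial test on the FAS.

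SAP 5.6 then gives the rules that decide membership: "Patient classification in the analysis sets is entirely based on protocol deviation and non-protocol deviation criteria". Two tables follow.

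- Table 5-4 lists protocol deviations. Entry-criterion violations such as "Patients meeting criteria for neuromyelitis optica" and "No diagnosis of MS as defined by 2010 revised McDonald criteria" lead to exclusion from the PPS only. Only the two consent codes, a missing consent date and "Incorrect ICF procedure", remove a patient from every set.
- Table 5-5 gives the rules by set. The FAS row has the two consent codes and, as criteria that are not protocol deviations, the lack of a valid randomisation number and "Randomization despite screen failure". The safety set row has the consent codes and "No double-blind study drug taken", and nothing about screen failure.

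The document history shows that the screen-failure criterion came in with Amendment 1 of 13 December 2019, before database lock. SAP section 4 lists five changes to the protocol's analyses; none concerns the FAS.

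**The concern.** A patient randomised despite screen failure has, by that description, been randomised. SAP 2.2 therefore includes the patient and Table 5-5 excludes the same patient. Because SAP 5.6 makes the tables decisive, Table 5-5 is likely to be what gets programmed.

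Three things follow. The population for the primary test would not be the one the protocol promises, and section 4 does not tell the reader so. Two programmers could build different FAS populations, because the SAP never says what counts as screen failure. And the exclusion spreads: SAP 2.2 builds the PPS and the extension FAS from the FAS, and the secondary efficacy analyses use it too.

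The planned placebo arm is 20 patients, so one exclusion there is 5% of the arm. SAP 2.2 requires major deviations for the PPS to be settled before unblinding. No equivalent sentence covers this criterion, which is classed as something other than a deviation.

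**Working it through.** **1. Membership under the two possible readings.** Reading A: screen failure means failing an entry criterion. Reading B: a number was issued in error to someone already recorded as a screen failure, who was never dosed.

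| Patient | SAP 2.2 | Table 5-4 | Table 5-5, FAS row | Table 5-5, safety row |
|---|---|---|---|---|
| A: randomised, fails a listed entry criterion (not consent), dosed | in FAS | in FAS, out of PPS | out of FAS | in safety set |
| B: randomised in error, never dosed | in FAS (untreated subjects are kept) | no consequence unless a listed code applies | out of FAS | out (no drug taken) |

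SAP 2.2 and Table 5-5 disagree on both rows. Tables 5-4 and 5-5 disagree only under Reading A.

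**2. The plan's power figure.** Inputs from SAP section 3: 40 and 20 patients, placebo rate 1.0 per scan, rate ratio 0.08, dispersion k = 4.5, one-sided alpha 0.025. SAP 2.5.1 gives 4 scans. Expected counts are 0.08 × 4 = 0.32 on ofatumumab and 1.0 × 4 = 4.0 on placebo.

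- Var(log RR) = (1/0.32 + 4.5)/40 + (1/4 + 4.5)/20 = 0.1906 + 0.2375 = 0.4281, so SE = 0.654.
- |ln 0.08| = 2.526, and 2.526/0.654 − 1.960 = 1.900, so power is 97.1%.
- With 54 evaluable patients (36:18), power is 95.6%.

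The stated power of more than 90% is reproduced. Simulating an unadjusted negative binomial fit (2,000 runs) gives about 95% with 60 patients and 94% with 54. All this counts four scans; with one scan per patient the same formula gives 85.5%, and 90.5% to 93.5% with other choices of null variance.

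**3. Effect of removing patients.** The documents give no number, so the counts below are assumptions.

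| Removed | Power (Wald) |
|---|---|
| none (40:20) | 97.1% |
| 1 ofatumumab (39:20) | 97.0% |
| 1 placebo (40:19) | 96.8% (rounded from 96.75%) |
| 2 (38:20 or 40:18) | 96.8% or 96.3% |
| 3 (38:19 or 40:17) | 96.4% or 95.8% |

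One patient is 1/60 = 1.7% of the trial, 1/40 = 2.5% of the ofatumumab arm or 1/20 = 5% of the placebo arm.

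**4. Effect on the estimate.** In 200,000 simulated placebo arms of 20 (mean 4, dispersion 4.5), dropping one patient at random moved the log placebo rate by 0.07 on average in absolute size and by 0.13 at the 90th percentile. Against an SE of 0.654, that is 0.07/0.654 = 0.11 and 0.13/0.654 = 0.20 standard errors. The signed mean was −0.007, so random removal produces almost no bias.

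**The case against.** The strongest reply is that screen failure is a disposition status, not a synonym for ineligibility. Protocol 6.1 uses the term for people who consented but did not go on to the next period, and SAP 2.3.1 counts those screened who never entered treatment. Table 5-5 places the criterion beside the lack of a valid randomisation number and outside the deviation codes. If every ineligible randomised patient were a screen failure, the entry-criterion rows of Table 5-4 would be redundant, because the PPS already excludes anyone not in the FAS. The narrow reading lets both tables work, and the safety row fits it, since never-dosed subjects are excluded there anyway.

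This stands as far as it goes. The conflict with Table 5-4 is conditional and should be stated that way. It does not remove the conflict with SAP 2.2, which keeps untreated randomised subjects, and the narrow meaning is nowhere written down.

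A reader might infer that the rule strips dosed, assessed patients from the primary analysis, or that it lets ineligibility found in data review decide who counts. The documents do not support either. No section says that the rule reaches dosed patients or late findings. Under Protocol 5.3 eligibility is confirmed before the randomisation system is contacted, the amendment predates database lock, and Protocol 5.4 keeps data analysts blinded until lock. A reader might also point to the concentration of lesions: in the simulation the most active placebo patient carried 37% of the arm's lesions on average. Nothing links the criterion to that patient.

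SAP 2.3.1 will report set sizes by arm, so an exclusion would show. The summary of reasons there covers protocol deviations, however, and this criterion is not classed as one.

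**Conclusion.** The point holds as a contradiction between the FAS definition in Protocol 9.1 and SAP 2.2 and the operative rule in Table 5-5, undeclared in SAP section 4 and resting on an undefined term. This needs no assumption about what screen failure means. The further conflict with Table 5-4 holds only if the term means failing an entry criterion.

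The effect on the result is unknown because the number of patients is not given. Under the design assumptions, losing up to three patients in the splits tried leaves Wald power at 95.8% or more, and one random placebo exclusion typically shifts the log rate by about a tenth of a standard error. The primary conclusion is therefore not shown to be at risk. What is at stake is whether the randomised comparison is the one promised and whether the FAS can be rebuilt from the text. It should be corrected, but it does not invalidate the primary analysis.

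**What to change.** Delete the screen-failure criterion from the FAS row of Table 5-5. If it is wanted, enter it in the PPS row, where it would no longer be inherited from the FAS. This costs one or two table cells and restores the stated population.

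If the sponsor wishes to retain a narrow rule, four changes are needed together:

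- Define it as covering only subjects randomised in error and never dosed, established from facts that predate randomisation and decided blind to treatment.
- Amend the FAS definition in SAP 2.2 to match. Without this, even the narrow rule contradicts the clause that keeps untreated subjects.
- List it in SAP section 4 as a change from Protocol 9.1.
- Add the primary model on all randomised patients.

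That costs a few sentences and one extra model run. The same edit could mention the two consent codes, which also remove randomised patients from the FAS without appearing in SAP 2.2, although there the two tables agree.

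If the Core analysis has already been run, as the dates in the document history suggest, the report should state how many patients the criterion removed in each arm and why, and show the all-randomised result beside the FAS result.

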5.7 Statistical method details for TEAEs

5.7.1 Odds ratios and 95% confidence interval

For an investigational drug group with n_1 patients at risk, independent from the control group with n_0 patients at risk, of whom x_1 and x_0 experience a certain event with probability π_1 and π_0 respectively, the odds ratio (OR) is estimated as

$$\frac{p_1 / (1 - p_1)}{p_0 / (1 - p_0)} \quad \text{with } p_1 = x_1/n_1 \text{ and } p_0 = x_0/n_0, \text{ simplifying to } \frac{x_1 \times (n_0 - x_0)}{x_0 \times (n_1 - x_1)}.$$

The OR and a conditional exact 95% confidence interval will be obtained by using the SAS procedure PROC FREQ with statement EXACT OR. The data set will include a patient level response variable indicating whether a patient has at least one AE of a specific type (1=yes, 0=no).

By default SAS sets the OR to missing if the odds for one of the treatments cannot be calculated (no infinity in SAS). This is problematic as infrequent but very serious adverse events that happen exclusively on active treatment can easily be missed if the OR for such highly imbalanced events is set to missing and sorted last. To ensure that potentially important imbalances appear at the top of a table if it is sorted by OR, the following additional rules are applied (considering the numerator and the denominator of the OR that would lead to divisions by zero):

- **NO CASE CLAUSE [0/0]:** If ($x_1=0$ and $x_0=0$) or ($x_1=n_1$ and $x_0=n_0$), i.e. there are either no events in both treatment groups, or all patients in both treatment groups had the event, then the OR cannot be estimated. The OR can be left missing for the sorting, but should be displayed on the output as “N.E.” indicating not estimable (if it has to be shown on the table, in this case it needs to be explained in the footnote).
- **SAFETY CLAUSE [~/0]:** If ($x_0=0$ and $x_1 \neq 0$) or ($x_0 \neq n_0$ and $x_1=n_1$), i.e. there are no events on control, but some on investigational drug, or everyone on investigational drug experienced the event, but not everyone on control, then OR will be imputed as 100000

for the sorting (so that it comes up top if sorted by the OR). On the output present the OR as ">100".

- EFFICACY CLAUSE[0/~]: If ($x_1=0$ and $x_0 \neq 0$) or ($x_1 \neq n_1$ and $x_0 = n_0$), i.e. there are no events on investigational drug, but some on control, or, everyone on control experienced the event, but not everyone on investigational drug, then OR will be imputed as 1/100000 for the sorting (so that it comes prior to the missing ones). On the output present the OR as "<1/100".

